## **OBJECTIVES/AIMS/HYPOTHESES**

The objective of this randomized control clinical trial is to provide data on the clinical impact of neurofeedback (NFB) treatment OEF-OIF-Operation New Dawn (OND) Veterans diagnosed with mTBI and experiencing persistent post-concussive symptoms as compared to a randomized control group, who will only receive usual care. Comparisons will be made at baseline, at the study treatment midpoint (around 4-6 weeks), and conclusion of study treatment (around 8-10 weeks) and at a two-month follow-up. The effect of NFB will be assessed on the following:

1. Frequency of headaches as measured by NEUROQOLTBI headache tool, and headache impact on functioning as measured by Headache Impact Tool (HIT-6)
2. Severity of sleep disturbance as measured by Insomnia Severity Index (ISI) and quality of sleep as measured by the NEUROQOLTBI Sleep disturbance tool.
3. Attentional functioning as measured by computerized visual attention performance test (QIKTest) accuracy index
4. Quality of life as measured by Quality of Life after Brain Injury (QOLABI) and NEUROQOLTBI Satisfaction with roles and activities & Ability to Participate in roles and activities.
5. General physical and emotional symptoms possibly co-occurring with mTBI as measured by self-report using General Symptom Scale (GSI), Depression, Anxiety and Stress Scale (DASS21), Post-Traumatic Stress Disorder Checklist (PCL), Patient Health Questionnaire-Depression (PHQ9), and NEUROQOLTBI Positive affect and wellbeing short form.

We aim to conduct a full-scale trial to determine whether NFB is a clinically relevant intervention in the care OEF-OIF-OND Veterans with mTBI who are experiencing chronic symptoms of headaches, insomnia and attention difficulties.

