
cosigned by a research team member for verification purposes. If the gift card(s) is mailed, staff will send the gift card(s) using a return receipt method (e.g., certified mail) to ensure delivery to the participant. A letter will be included with the mailing. The letter will list the visit date(s) and type (e.g., assessment, treatment) associated with the gift card(s). Staff will maintain contact with the participant (e.g., phone call advising of mailing date) to help ensure successful delivery. The return receipt will be filed with the participant's study chart. If the gift card(s) is delivered electronically, the message will include a table with a list of the visit date(s) and type (e.g., assessment, treatment) associated with the gift card(s). The message will ask the participant to reply to the message to acknowledge receipt of the gift card(s). The message will be saved and filed with the participant's study chart.

In addition, interventions will be offered at hours and days that would enable Veterans who work to participate. Phone calls will be made as session reminders, the week and day before as well as on the day of appointment. In addition, a paper monthly calendar with the appointments indicated that can be hung on the wall will be given as well as an appointment card at the end of each session. In addition, those in the control group, will be offered NFB training, after they complete the control group requirements.

**Outcome Measures:** Outcome measures will be used to compare the results of the NFB intervention and control group. Statistical tests and analyses will be conducted to determine the existence of statistical differences between the intervention and control group measures and on the measures at pre-treatment, midpoint, and immediate post treatment for determination of clinical improvement.

To determine the impact of NFB, the following assessment tools (see Table 4) will be administered at baseline, 4-6 weeks (midpoint of treatment), and 8-10 weeks (conclusion of treatment) and 2 months following completion to the control and intervention mTBI groups.

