
At the end of the consenting process, participants will be randomized into one of the study groups (NFB or Control). Those participants assigned to the intervention group will be scheduled for the initial, 4-6-week, 8-10-week and 2-month follow-up assessments as well as for the 10 weeks of intervention sessions: up to 5 1-hour (but usually 3) NFB training sessions a week. Participants assigned to the control group will be scheduled for 4-6-week, 8-10-week and 2-month follow-up assessments.

**Communication with Participants:** Study staff will contact enrolled participants via multiple methods including, face-to-face communication, telephone call, mailings (e.g., US postal service), electronic mail (e-mail) and My HealtheVet Secure Messaging. Participants will have the option to use any, all, or a combination of the communication methods. Participants are generally contacted for appointment reminders, gift card disbursement, or other research-related information. All ORD guidelines regarding the use of electronic mail and My HealtheVet secure messaging will be followed. Research staff will be careful with the frequency of contacts to participants to avoid any perceived coercion or harassment. Electronic and mailed communications will be saved in accordance with the VHA Record Control Schedule (RCS 10-1).

For e-mail communication, a study-specific Outlook mailbox account or other appropriate research staff Outlook account will be used to send and receive messages. All necessary precautions will be put in place to not transmit PII/PHI to participants and to not identify the research study. Generic, standard Subject lines will be used to not disclose any PII/PHI. For example, appointment reminders will use the subject line, "Appointment Reminder." See Appendix A for example phrases for e-mail use.

For My HealtheVet Secure Messaging, a study-specific group will be created for use in the study. Although VA sensitive information is allowed with secure messaging, research staff will use the least amount of PII/PHI information necessary in the message. See Appendix A for example messages for My HealtheVet Secure Messaging use.

**Volunteer identification and confidentiality:** Participants will not be identified in any presentation of the results. The initial form with contact information and last four of the participant's SS# that will be used for appointment, reminders and charting purposes will be kept in a locked file cabinet in either E-wing 4A-100 or

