Participants can rescind their consent about their study information and contact information for future study use at any time upon communication with the primary investigator. If participants agreed to have their de-identified data kept for future use, but later rescind this consent, these data cannot be removed since they are de-identified and no linkages are possible.

**Informed Consent Ability:** The population for this study will not include individuals that cannot provide informed consent.

**Assent:** Not applicable to this population. No children are included in this study.

**Randomization - Assignment Process into Control or Intervention Groups:** A blocked randomization schedule will be created at the beginning of the study with randomly selected block sizes of 4. The randomized block size will prevent study personnel from predicting treatment assignments for potential participants. The individual assignments of the randomization schedule will be placed in sequentially numbered opaque envelopes that will only be opened as new participants are enrolled into the study

**Enrollment:** Enrollment will be completed when the potential participant is randomized into one of the study groups.

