## Statistical and Data Analysis Plan

The analyses will be conducted based on intention-to-treat principle (Friedman, Furberg, DeMets, 2010) where participants are analyzed according to their group assignment regardless of the treatment received (e.g., switching treatments or poorly adhering to assigned treatment). Patient demographics will be presented using frequencies and percentages for categorical variables and means and standard deviations for continuous variables. Although balance between intervention arms will be guaranteed by randomization, there may be unmeasured confounding. Two sample t tests or chi-square tests will be conducted to investigate potential confounding effects on demographic variables.

For each hypothesis, first two sample t-tests will be utilized to assess the effect of NFB intervention at each time. Then, a repeated-measures analysis of variance (ANOVA) will be implemented for the outcome variable that shows significant group effect. The mixed effects model will include group (between-factor), time (within-factor), and the interaction between group and time as fixed effects. From this model, the interaction will allow the testing of whether longitudinal trajectory is associated with group assignment. The longitudinal trajectory from baseline, 4-6-week and 8-10-week to 2-month follow-up, for each outcome of interest will be investigated in this model accounting for covariance structure (e.g., AR(1)) within participants. This determines the rate of improvement during the course of the intervention. Any baseline subject characteristics found to differ between groups as covariates to assess the impact of the baseline covariates on the effectiveness of the intervention over the course of the study will also be included if needed].

The outcomes of interest for each hypothesis are clinically significant:

- 1) Reduction in frequency, severity and/or impact of headaches: HIT-6 and NEUROQOLTBI
- 2) Improvement of perceptions of quality of sleep and insomnia severity: ISI and NEUROQOLTBI Sleep disturbance
- 3) Improvement in attention function: QIK-Test
- 4) Improvement in the quality of life: QOLIABRI and NEUROQOLTBI Satisfaction & Participation in roles and activities

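### One stated block size of 4 does not support the claim that assignments cannot be predicted; baseline is not excluded from the t-test selection step; and the protocol contradicts itself on whether baseline precedes randomisation.

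*Combined protocol and SAP*

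**What the plan says.** **Blocks.** The section on assignment to control or intervention describes a schedule with "randomly selected block sizes of 4" and sequentially numbered opaque envelopes. It then states: "The randomized block size will prevent study personnel from predicting treatment assignments for potential participants". No second size is named.

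**Selection of outcomes.** The Statistical and Data Analysis Plan says: "For each hypothesis, first two sample t-tests will be utilized to assess the effect of NFB intervention at each time". A repeated-measures model "will be implemented for the outcome variable that shows significant group effect". It does not say which visits count. The Objectives section reads "Comparisons will be made at baseline, at the study treatment midpoint" and goes on to list the end of treatment and the two-month follow-up.

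**Order of baseline and randomisation.**
- *Baseline first.* The opening text of Pre-Enrollment and Enrolled Procedures counts the baseline session as pre-enrolment and leaves three further assessments for after enrolment. The Enrollment paragraph says "Enrollment will be completed when the potential participant is randomized into one of the study groups". Together these put baseline before randomisation.
- *Randomisation first.* Consenting Procedures randomises when consenting ends, and the Consenting Visit paragraph schedules baseline after consent. Table 6 puts randomisation at -1 week under pre-enrolment and baseline at 0 weeks under enrolled participants. The baseline visit is described under the heading for enrolled participants.
- *Tables.* Table 5 puts the initial assessment at -1 week; Table 6 puts baseline at 0 weeks.

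**The concern.** The block sentence credits the trial with a protection that one block size cannot give, and it could pass unchanged into the report's account of allocation concealment. Arms are visible to staff (training sessions against weekly phone calls), and the principal investigator is also one of the neurofeedback specialists.

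Read literally, testing at each time includes baseline, so a baseline difference could bring an outcome into the longitudinal model. Such a difference can arise by chance. It can also arise if participants already knew their arm when they answered, which is why the order matters. Of the 13 outcome scales listed in the analysis plan, 12 are self-report; the exception is the QIKtest. Having a coordinator or assistant run the assessments does not blind a self-report. The group-by-time interaction uses baseline, so an arm-related shift there would move the interaction, by an amount and in a direction that the documents do not indicate.

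**Working it through.** The plan gives no figure for predictability or for the error rate of the selection step, so there is none to reproduce. Its 0.49 SD (Power paragraph) serves below only as an effect size for costing the fix; whether it is attained at the stated power is a separate matter.

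**1. Predictability with blocks of 4**

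Inputs: block size 4 and 1:1 allocation (36 per arm). Assumption: the observer knows the size and all earlier assignments.

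A block has six equally likely orders. In AABB and BBAA the last two assignments are certain; in the other four orders only the last is.

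- Certain share: (2×2 + 4×1)/6 = 1.333 of 4 = 33.3%. That is 24 of 72 completers, or about 33 of the 100 who may be recruited.
- Best guess by position: 1/2, 2/3, 2/3 and 1. The sum is 2.833, and 2.833/4 = 70.8%.

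Comparison with varying sizes (assumed; none is in the plan), from 1,500 simulated lists of 72 and an observer who knows the set of sizes and updates after each assignment:

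| Sizes | Certain | Best guess correct |
|---|---|---|
| 4 only | 33.3% | 70.8% |
| 4, 6 | 5.5% | 69.1% |
| 2, 4, 6 | 4.0% | 70.1% |
| 4, 6, 8 | 2.3% | 67.9% |

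Varying the size removes most of the certainty but little of the general guessability.

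**2. Selection step**

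Inputs: 36 per arm, four visits, correlation 0.6, two-sided 0.05. Each simulated trial runs a t-test at each visit, then the 3-df group-by-time test with a covariance structure matching the data. There are 60,000 trials per setting and no true effect. Results are equal correlation / AR(1):

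| Quantity | Baseline counts | Baseline excluded |
|---|---|---|
| Outcome enters the model | 14.6% / 15.5% | 11.9% / 12.2% |
| Entry plus significant interaction, no shift | 2.3% / 2.8% | 1.8% / 2.2% |
| Same, assumed baseline shift 0.1 SD | 3.1% / 3.6% | 2.0% / 2.4% |
| Same, assumed baseline shift 0.2 SD | 6.9% / 6.8% | 3.2% / 3.4% |

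Repeat runs move the no-shift figures by about 0.1 percentage point.

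Power for entry plus a significant interaction at 0.49 SD (20,000 trials, no shift), with baseline counted and then excluded:
- 0.49 SD at all three post-baseline visits: 54.5% to 52.6% (equal correlation); 45.3% to 44.1% (AR(1)).
- 0.245, 0.49 and 0.49 SD: 48.3% to 46.4%; 30.4% to 29.4%.

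**3. Order**

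No arithmetic applies. If enrolment is completed by randomisation and baseline is pre-enrolment, baseline comes first. If randomisation closes the consenting process and baseline is a later visit for enrolled participants, randomisation comes first. Both cannot hold. The conflict lies in the running text as well as in the tables, so it does not depend on how the tables were extracted.

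**The case against.** **Blocks.** The wording may mean blocks of 4 in random order. Opaque numbered envelopes hide the next assignment, certainty requires close tracking, and best-guess accuracy hardly changes. All of this is fair. But random order does not randomise the block size, which is the reason the plan gives, and envelopes do not stop deduction near the end of a block. A reader might infer that allocation was actually subverted; nothing in the documents shows this.

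**Selection.** The tests are described as assessing the effect of the intervention, which cannot exist at baseline, so a sympathetic reader would exclude it. The Outcome Measures sentence that mentions pre-treatment can be read as within-group improvement and is weak support for a baseline comparison between arms. Without a shift the effect is about half a percentage point. This makes it a clarification, but one the plan needs, because the Objectives section does name baseline among the comparisons.

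**Order.** A reader might infer that the timing of the control baseline is unstated, because Consenting Procedures lists an initial assessment only for the intervention arm. The documents do not support that. Table 1 pays controls for baseline, the Challenges section pays all subjects for the pre-treatment assessment, and Table 5 covers both groups. Table 6 and the enrolled-participants section place baseline after randomisation without separating the arms. The timing is stated and then contradicted.

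**Remedy.** It is tempting to rest the conclusion on post-baseline t-tests if baseline was unblinded. That would be worse. At least one of the three is significant under the null about 12% of the time per outcome (the entry rate above). An assumed constant prognostic imbalance of 0.2 SD, the kind that predictable allocation could cause, makes a single one falsely significant 13.3% of the time (noncentral t, 70 df, noncentrality 0.2×√(36/2) = 0.849) but leaves the group-by-time interaction unshifted. The hypotheses also concern change in scores.

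**Conclusion.** All three parts hold, at modest size.

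1. The unpredictability claim is unsupported as written. One third of assignments are certain, given knowledge of the size and of past assignments. The loss relative to varying sizes is in certainty, not in overall guessability.
2. The role of baseline in selecting outcomes is open. The harm is small without a baseline shift and roughly doubles the error (about 7% against 3%) at 0.2 SD. That shift is an assumption; the documents give no figure. The results also rest on 36 per arm and correlation 0.6.
3. The order of baseline and randomisation is contradictory. If allocation came first, self-reported baselines were given with the arm known, and this limits how far the group-by-time result can be trusted.

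This should be corrected before analysis. It does not show that assignments were manipulated or that the interaction is biased in a known direction, and it gives no reason to replace the planned longitudinal comparison.

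**What to change.** The Data Protection paragraph says participant procedures are complete, so only text, records and reporting can change.

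- **Randomisation section:** state the block size or sizes actually used. If only 4, delete the unpredictability sentence and do not make the claim in the report.
- **Statistical and Data Analysis Plan:** state, before analysis, that only the three post-baseline t-tests count for selecting outcomes.
- **Order:** reconcile Pre-Enrollment and Enrolled Procedures, Consenting Procedures, Enrollment, the enrolled-participants section and Tables 5 and 6 to the order actually used, confirmed from existing allocation and baseline dates in each arm. If baseline followed allocation, report that self-reported baseline was collected with the arm known, and give this as a limitation of the group-by-time result.
- Do not move the effect conclusion to unadjusted post-baseline t-tests.

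The cost is wording, a check of dates already on file, 1-2 percentage points of power from the selection change, and possibly a less favourable statement on allocation concealment.

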### **Study Procedures for Enrolled Participants**

**Initial Baseline Assessment Session Visit (approximately 2.5 hours):** Participants will be given preparation instructions to ensure optimum test results and will be instructed to have adequate rest the night before and to have eaten a regular meal or snack prior to the test session. There will be an attempt to schedule assessment session during the period when they report maximum alertness. One of the tests, the attention QIKtest will be administered early in the assessment session to minimize test fatigue. The participants will also complete several other questionnaires (see Table 5) during this baseline visit in addition to the demographic form will include pregnancy status (or plans to become pregnant in the next five months) co-morbid health issues, description of headache, insomnia, and attentional disorder, experience with biofeedback, and participation in co-occurring classes or therapies, list of current medications, and ethnicity. Although the total time for completion of the questionnaires is estimated to be 120 minutes, a 2½-hour time frame is given for rest

periods, water break, slow test takers, and the answering of any questions the participants may have. Assessment session visits will be conveniently scheduled.

**Mid (4-6-week), End of Treatment (8-10-week) and 2-Month Follow-up Assessment Sessions (2.5 hours each session):** As above in the baseline assessment, participants will be given preparation instructions to ensure optimum test results. Participants will be instructed to have adequate rest the night before, and to have eaten a regular meal or snack prior to the assessment sessions. There will be an attempt to schedule all sessions at the same time of day for each individual participant, during a period of maximum alertness. One of the tests, the attention QIKtest will be administered early in the assessment session to minimize test fatigue. The participants will also complete several other questionnaires (see Table 5) during these 3 assessment sessions. In addition, the participants will indicate any changes on the demographic form, including changes in pregnancy status (or plans to become pregnant in the next five months) co-morbid health issues, participation in co-occurring classes or therapies and medications. Although the total time for completion of the questionnaires is estimated to be 120 minutes, a 2.5-hour time frame is given for rest periods, water break, slow test takers, and the answering of any questions the participants may have. Should a participant be unable to complete any assessment visit in person, the questionnaires may be mailed to the participant and mailed back at no cost to the participant. Decision to mail the questionnaires will be made by the study team on a case-by-case basis. The QIKtest cannot be mailed therefore this missing data point will be accounted for statistically at final analysis. Instructions will be mailed with the packet. See Appendix B for an example of the general information to be sent to the participants.

**Participation Termination by the Principal Investigator:** Possible reasons for study participation termination by the PI without concurrence by the participant include: concern for the individual's health and/or safety and participant non-compliance with study procedures (e.g., excessive number of missed NFB and/or assessment appointments; non-responsive to outreach attempts for rescheduling; non-responsive to control group phone calls.) Participants will be informed of this decision either in person, via telephone, or via letter. Participants who are terminated could enroll at a later date if they desire. However, the research team will review these requests on a case-by-case basis.

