5	Quality of Life After Brain Injury QOLIBRI	Reliability: Cronbach's Alpha 0.75-0.95 Test-retest $r = 0.73$ . Validity: Sensitivity 75% Specificity 75%	A 37-item instrument consisting of 6 scales measuring cognition, self, daily life and autonomy, social relationships, emotions, and physical problems. Designed to measure quality of life specific for TBI. (37 items, 15 min)	Objective 4. Provide data on the impact of NFB training as compared to control on Veterans' Quality of life related to mTBI
6	General Symptom Inventory (GSI)	Used in clinical practice- was found to be very useful in the ongoing assessment of key symptoms while undergoing NFB sessions	Self-report instrument of symptoms in 7 categories including sleep, attention and learning, sensory, behavioral, emotional, physical, and pain (less than 10 min). [Note: In addition to the assessment schedule, an abbreviated symptom list will be used by neurofeedback specialist at each session to assist with treatment planning.]	Objective 5. Provide data on the impact of NFB training as compared to control on Veterans' General physical, neurobehavioral, and emotional symptoms
7	Depression, Anxiety and Stress Scale – 21 (DASS21)	Reliability: Cronbach's Alpha 0.93 Validity: $r = 0.73- 0.85$	DASS21 is a set of three self-report scales designed to measure the negative emotional states of depression, anxiety and stress. (21 items, less than 10 minutes.)	Objective 5. Provide data on the impact of NFB training as compared to control on Veterans' General emotional symptoms
8	Demographic Data Form	No validity or reliability data available	Age, gender, all current medical diagnoses, relevant symptoms to study, all current medications, current therapeutic classes & treatments, medical board status and previous experience with biofeedback. (2-10 min)	Objective 5. To assess variables impact on treatment (also determination of initial eligibility to participate in study)

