## 5) Improvement in the general physical and emotional symptoms: GSI, DASS21, PHQ9, PSL-5 and NEUROQOLTB Positive affect and wellbeing.

As a secondary analysis, a per-protocol analysis will investigate the effect of the intervention in participants that adequately adhere to the intervention, e.g., participants that attend over half of the treatment sessions versus participants attend less half of the treatment sessions. For all analyses, model assumptions will be evaluated with graphical and formal statistical tests such as Kolmogorov-Smirnov goodness-of-fit test. If there is marked nonlinearity or non-normality, transformation of the dependent variable or using a different link function such as the log link function will be considered. All analyses will be done in SAS version 9.4 on a non-VA Computer with two-tailed tests and P-value < 0.05 will be considered statistically significant.

Other statistical analyses not run by the biostatistician will be completed by the research team within the VA Informatics and Computing Infrastructure (VINCI) workspace.

**Power:** Power: Literature on NBF studies of patients with TBI have reported dropout rates ranging from 10% to 30% (Nelson & Esty, 2012; Zoeful, Huster, & Herrmann, 2011). Assuming a dropout rate of 28% and a moderate autocorrelation of 0.6 among repeated measures, this sample size will ensure to detect at least significant difference of 0.49 standard deviation with a power of 80% in the NFB intervention group compared to the control group with two-tailed significance level of 0.05 based on Diggle's et al (2002) approach for 4 repeated measures. This indicates that differences of less than 15% can be detected for HIT-6 (5.8% based on Cerritelli, 2015) and QOLABRI (13.8% based von Steinbuechel et al, 2016) and less than 26% for ISI (17.9% based on Nguyen, 2017) and DASS21 (19.7% based on Arundine et al., 2012) questionnaires. Thus, differences of 15% to 25% in the study instruments would be clinically significant. In addition, this study will detect a difference of at least 0.67 standard deviation if multiple testing is adjusted using FDR, which also provides a moderate effect size.

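### The promise to account statistically for missing QIKtest values is not kept by the per-visit t-test that decides each outcome; an ungated likelihood mixed model would keep it

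*Combined protocol and SAP*

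**What the plan says.** Under Study Procedures for Enrolled Participants, a participant who cannot attend the mid, end or 2-month visit may return the questionnaires by post: "Decision to mail the questionnaires will be made by the study team on a case-by-case basis". The computerised attention test cannot be done that way, and the text continues: "The QIKtest cannot be mailed therefore this missing data point will be accounted for statistically at final analysis". This is the only statement in the documents about handling missing outcomes.

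The Statistical and Data Analysis Plan opens with "The analyses will be conducted based on intention-to-treat principle", explained as meaning that "participants are analyzed according to their group assignment regardless of the treatment received". It then says: "For each hypothesis, first two sample t-tests will be utilized to assess the effect of NFB intervention at each time". A repeated-measures ANOVA, also described as a mixed effects model with group, time and their interaction and a within-participant covariance structure such as AR(1), follows only for an outcome with a significant group effect. No imputation, missing-data assumption, estimation method or missing-data sensitivity analysis is named.

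The Power paragraph begins: "Assuming a dropout rate of 28% and a moderate autocorrelation of 0.6 among repeated measures". The 28% is used only to size the trial (up to 100 recruited so that 72 complete).

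**The concern.** The step that decides which outcomes go forward is the one that makes no use of partial data. A t-test at one visit compares only the people measured at that visit. It is unbiased if loss is unrelated to outcome or acts alike in the two arms. It is not if, say, NFB participants who are doing poorly at mid-treatment tend to stop while control losses are haphazard.

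Some features of the design make loss that differs by arm plausible, though none shows it. Treatment is not masked. The study team decides on mailing. NFB participants attend 20 on-site sessions while controls receive calls. The grounds for termination by the PI include missed NFB appointments in one arm and unanswered calls in the other. Controls are offered NFB only after their final assessment, an incentive to stay that the NFB arm lacks.

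The QIKtest carries the most exposure. It is the sole measure for hypothesis 3, the only performance test in Table 4, and the only outcome lost whenever a visit is mailed.

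**Working it through.** **Inputs from the documents.** 36 completers per arm; up to 100 recruited; 28% dropout (literature range 10% to 30%); correlation 0.6; four measures; two-sided 0.05; AR(1) as the example covariance.

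**The plan's own figures.** 72 / (1 − 0.28) = 100, as stated. Detectable difference = (1.960 + 0.842) × √(2f/n), where f is the variance factor for combining four correlated measures. With AR(1) at 0.6 and generalised least squares, f = 0.571, so at n = 36 the result is 2.802 × √(1.143/36) = 0.499 SD, close to the stated 0.49. (An exchangeable correlation gives f = 0.70 and 0.552 SD.) The stated figure therefore belongs to a four-measure longitudinal analysis. One per-visit t-test has f = 1: 2.802 × √(2/36) = 0.660 SD.

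**Who is in each t-test.** Of 50 randomised per arm, 28% loss leaves 36. Mailed visits remove further QIKtest values, at a rate the documents do not give. The t-test does not use the earlier scores of those missing.

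**Size of the bias (assumed mechanisms).** No true effect, normal scores with higher meaning worse, 50 per arm, 28% lost after the mid visit. In the NFB arm the log-odds of loss rise by 0.5 to 1.2 per SD of mid score.

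A hand check of the steepest case, with random loss in controls: those lost would have ended 0.58 SD worse than those kept, so the mean of those kept is too good by 0.28 × 0.58 = 0.16 SD. Under AR(1) the correlation from mid visit to 2-month follow-up is 0.6² = 0.36, so the bias there shrinks by 0.36/0.6 = 0.6, giving 0.16 × 0.6 ≈ 0.10 SD.

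Simulation results for the t-test (8,000 or 20,000 trials per row; at 8,000 the Monte Carlo standard error of a 5% rate is √(0.05 × 0.95/8000) = 0.24 points):

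| NFB slope | Control loss | Correlation with mid score | Bias towards NFB | False positives |
|---|---|---|---|---|
| 1.2 | random | 0.6 | 0.16 SD | 10.5% |
| 1.0 | random | 0.6 | 0.14 SD | about 9% |
| 0.5 | random | 0.6 | 0.08 SD | about 6% |
| 1.2 | random | 0.36 (AR(1), 2 months) | 0.10 SD | about 7% |
| 0.5 | random | 0.36 (AR(1), 2 months) | 0.04–0.05 SD | 5.2–5.8% |
| 1.2 | slope half as steep | 0.6 | 0.065 SD | 6.0% |
| 1.2, only 10% lost | random | 0.6 | 0.063 SD | 6.4% |
| same pattern in both arms | same | 0.6 | 0 | 4.8% |
| random | random | 0.6 | 0 | 5.2% |

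Across the same settings, with control loss half as selective as NFB loss, the bias is about 0.03 to 0.07 SD and the false-positive rate no more than about 7%.

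**The alternative.** In 600 trials of the steepest case, a likelihood mixed model on all observed visits gave 0.009 SD bias and 5.7% false positives, against 0.148 SD and 10.7% for the t-test. The standard error of a 5% rate at 600 trials is √(0.05 × 0.95/600) = 0.9 points, so 5.7% is compatible with 5%.

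**The case against.** The strongest reply is that the plan already contains the remedy. Its mixed model, fitted by likelihood, keeps participants with partial data under missing-at-random. A reader might infer that nothing in the plan addresses missing values; that would be wrong. What remains is narrower. The model is reached only through a significant t-test, and its fitting method is unstated. It is also called repeated-measures ANOVA, which in its classical form discards incomplete participants.

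A reader might also infer a breach of intention-to-treat. The documents do not support this: their wording covers analysis by assigned group and says nothing about missing outcomes. Nor are people dropped from the trial. Each leaves only the tests at the visits missed, and someone assessed by mail still supplies every questionnaire.

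The magnitudes rest on assumptions. The simulation models general dropout, not mailed visits, and the larger figures need strong selection in one arm only. Both arms have the same assessment schedule and the same graduated assessment payments, which argues against very different loss. QIKtest scores may also be skewed (pilot entry mean 13.00, SD 17.53, n = 4), whereas the simulated scores are normal. These points stand, and they limit the claim about size. They do not supply the missing step.

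**Conclusion.** The point holds as a mismatch between a commitment and the test that decides. QIKtest values lost to mailed visits are to be dealt with in the analysis, yet the deciding test for every outcome omits anyone not measured at that visit, and the one method able to use partial data sits behind it.

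The consequence is conditional. With 28% loss that depends on mid-treatment score in the NFB arm only, bias is about 0.04 to 0.16 SD and the false-positive rate about 5.5% to 10.5%. It is smaller when control loss is partly selective and absent when loss is alike in both arms or random.

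It would be tempting to say that the plan doubles the false-positive rate, or that mailing biases the QIKtest result. Neither follows. The doubling is the upper end of an assumed range, and the documents give neither a loss mechanism nor a mailing rate.

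**What to change.** In the Statistical and Data Analysis Plan:

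- Remove the t-test gate. Make the group-by-time mixed model, fitted by REML to all randomised participants with any outcome data, the assessment of effect for every outcome, with the group difference at each visit estimated from it.
- State the missing-at-random assumption.
- Report missingness and mailed visits by arm and visit.
- Add one sensitivity analysis for data not missing at random, for example control-based imputation.

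In the assessment-session text, cite this model as the handling of missing QIKtest values. Multiple imputation that adds the GSI attention and QOLIBRI cognition scores from the same mailed visit is optional; the documents give no correlation between these scores and the QIKtest.

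The cost is an amendment to the analysis wording and minor SAS programming, with no new data. The price in method is reliance on missing-at-random, which the sensitivity analysis probes. The Data Protection section says participant procedures were complete as of March 2025, so the analysis is where this can still be changed. The documents do not say whether analysis has begun; the amendment should be dated before outcomes are compared by arm.
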